### 3.3. Setting

The study will be conducted in the following four centres: Barau Dikko Teaching Hospital Kaduna State University (BDTH), Ahmadu Bello University Teaching Hospital Zaria (ABUTH), National Hospital Abuja (NHA), and Federal Medical Centre Katsina (FMC).

### 3.4. Sampling strategy

Random and purposive sampling technique.

## 4. Inclusion and exclusion criteria

The following inclusion criteria will apply for patients/parents:

- Aged  $\geq 18$
- Have SCD diagnosis or having a child with a SCD diagnosis
- Attending the centre from at least 6 months
- Nigerian nationality
- Informed Consent signed

The following inclusion criteria will apply for healthcare professionals:

- Working in a SCD clinic
- At least 5 years of experience with SCD patients
- Informed Consent signed

The following exclusion criteria will apply for all participants:

- Informed consent form withdrawal
- Illiterate subjects
- Any psychiatric conditions impairing the participation in this study.

## 5. Study procedure

### 5.1. Questionnaire completion

After obtaining the informed consent, subjects (patients, parents/legally designated representatives and healthcare professionals) will be asked to complete the questionnaire. Two questionnaires have been developed, one addressed to patients, parents, legally designated representatives (Annex I) and another one for healthcare professionals (Annex II)

The following measures will be adopted to reduce the interviewer effect:

- The investigator will give instructions to complete, but questionnaires will be self-completed.
- Participants will have time to complete the questionnaire in a private setting.
- Completed questionnaires will be blindly deposited in a closed box. This will be thus safeguarded by the investigators.
- Completed questionnaires will be returned to the coordinating investigator for analysis.

Questionnaires will be pseudonymised: an alphanumeric code will be indicated on each questionnaire and reported on the corresponding informed consent form.

All the study investigators are researchers/officers in the centres not involved in patients' clinical management. The veracity and consistency of responses are of paramount importance for the

---

validity of the study and the improvement of the management of SCD patients: all the actions necessary to allow the participants to freely express themselves will be adopted.

Together with the questionnaire, participants will receive information about the time and venue for the focus group discussion (Annex III). For those who are willing, reminders about the focus group will be sent by e-mail/phone.

### **5.2. Focus group**

A 45-60 minutes discussion will be scheduled with patients and parents, according to details given in the attached guidance. The principal investigator of each centre will lead the focus group discussion, leaving the possibility to everyone to freely express his/herself.

### **5.3. Data collection**

Data will be collected and transcribed by the coordinating investigator in an Excel file that will be used for analysis.

### **5.4. Data analysis**

Data will be managed by the study investigator, his delegates and authorised people (e.g. the hosting institution staff, statisticians, IT people). Data will be analysed by the coordinating investigator. SPSS and Thematic Analysis will be performed.

## **6. Timeline and milestones**

### **6.1. Start of data collection**

March 2020

### **6.2. End of data collection**

September 2020

### **6.3. Final report of study results**

October 2020

---

## 7. Ethics and data protection

This research is going to obtain approval from ethics committee, both NHREC and local. No invasive procedures will be performed. Personal data as well as special categories of personal data such as health data will be processed within this study. Specific consent will be got to use these data for research purposes. Aggregated data may be shared among institutions belonging to the ARISE Consortium after stipulating a Data Sharing Agreement (DSA). Data will be shared with academia and the broader community (e.g. conferences, articles, seminars, dissertation, reports) once anonymized. Data and recordings will be stored until December 2022,31st in Barau Dikko Teaching Hospital, Kaduna State University. At the end of the storage period data will be made anonymous and the recordings destroyed. After the end of the project, only anonymised data may be processed. Finally, a Data Protection Impact Assessment (DPIA) for the study was conducted under Article 35 of the European General Data Protection Regulation and was included as Annex in Deliverable 8.9 indicating that the processing activities do not result in a high risk for data subjects.

## Annex I. QUESTIONNAIRE FOR NEED ASSESSMENT OF PATIENTS/PARENTS INVOLVED IN SICKLE CELL DISEASE MANAGEMENT

Questionnaire code: \_\_\_\_\_

### SECTION A

#### Bio Data

1. State \_\_\_\_\_
2. Local Government \_\_\_\_\_
3. Name of SCD Clinic/Hospital \_\_\_\_\_
4. Age \_\_\_\_\_
5. Gender Male [ ] Female [ ]
6. Education: University [ ], Secondary [ ], Primary [ ], Nursery [ ] Other (please specify) \_\_\_\_\_
7. Occupation: Business [ ], Civil Servant, [ ], Farmer [ ], Other (please specify) \_\_\_\_\_

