### 3.2. Sample size determination

As pilot experience, the questionnaires will be administered to 30 SCD patients or parents/legally designated representatives of children affected by SCD and 30 Professionals working with SCD patients (mainly doctors and nurses) in each centre for a total of 120 patients and 120 health workers. A focus group discussion will be run with the SCD patients/parents. Following the pilot study, a wider survey will be launched involve patients, parents and healthcare professionals in the whole country and in other centres involved in the project.

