### SECTION B

- 1. If you are a patient, what is your diagnosis? If you are a parent, what is the diagnosis of your child?**
  - A. Sickle cell disease [ ]
  - B. Sickle cell/b-thal [ ]
  - C. Sickle Beta-Plus Thalassemia [ ]
  - D. Other (please specify) \_\_\_\_\_
- 2. How is your/your child current transfusion regime?**
  - A. I am not transfused [ ]
  - B. I am regularly transfused [ ]
  - C. I am occasionally transfused [ ]
  - D. Other (please specify) \_\_\_\_\_
- 3. Where do you usually get information about Sickle Cell Disease?**
  - A. Websites
  - B. Social Networks
  - C. Scientific journals
  - D. TV
  - E. Radio
  - F. Leaflets/booklets
  - G. Doctor/nurse
  - H. Other patients
  - I. Relatives/friends
  - J. Religious leaders
  - K. Other (please specify) \_\_\_\_\_

---

**4. Please, indicate your main information source:** \_\_\_\_\_

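### Annex I, Section A, items 4-7 do not say whether a parent or representative should describe themselves or the child, and the child's age and gender are asked nowhere

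*Protocol*

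**What the plan says.** Protocol section 5.1 describes two questionnaires, "one addressed to patients, parents, legally designated representatives (Annex I") and one for health professionals (Annex II). On completion, it states: "The investigator will give instructions to complete, but questionnaires will be self-completed".

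Section 4 admits to the patient/parent group people aged 18 or over who "Have SCD diagnosis or having a child with a SCD diagnosis", and excludes "Illiterate subjects". Section 3.2 sets the group in each centre as "30 SCD patients or parents/legally designated representatives of children affected by SCD", with no split between the two kinds of respondent.

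In Annex I, Section A (Bio Data), items 4 and 5 are bare labels for age and gender. Item 6 is "Education: University [ ], Secondary [ ], Primary [ ], Nursery [ ] Other (please specify") and item 7 is "Occupation: Business [ ], Civil Servant, [ ], Farmer [ ], Other (please specify"). None names a person. Section B does name the person in its first item: "If you are a patient, what is your diagnosis? If you are a parent, what is the diagnosis of your child"? Several later items also refer to the respondent or the respondent's child.

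**The concern.** Every parent form involves two people: the adult holding the pen and the child with the disease. Section B acknowledges this and Section A does not. The item on education offers a level suited to a small child, while the item next to it offers only adult occupations, so neighbouring items point to different people.

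Two things are at stake. First, the columns for age, gender, education and occupation may hold the respondent's details on some parent forms and the child's on others, with no reliable way to tell which. Second, whichever reading a parent takes, one person's age and gender are lost. Because the questionnaire is fixed in the protocol, no later analysis plan can recover what was never asked. The study is descriptive and is a pilot for a wider survey, so a defect in the form could be carried forward.

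**Working it through.** The protocol gives no figure for this point, so the check is mainly a comparison of texts.

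**1. Who can fill in the form.** Sections 3.2, 4 and 5.1 together allow an adult patient, a parent or a legally designated representative. All must be at least 18 and able to read.

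**2. Whom items 4-7 describe.** No possessive or instruction is printed. Education includes a nursery level, which is an unlikely attainment for a literate adult. Occupation offers business, civil service and farming, with no pupil or student option.

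**3. Whom Section B describes.** Item 1 separates patient from parent in its wording, but its answers are diagnoses only, so it does not record which applies. Item 2 asks about the respondent or the child, yet its options are phrased in the first person as if the patient were answering. Item 21 asks who pays for the respondent's own treatment. A parent is thus already led to answer some items in the patient's place.

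**4. What each reading yields on a parent form.**

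| Reading of items 4-7 | Respondent's age and gender | Child's age and gender |
|---|---|---|
| Parent describes self | recorded | not recorded |
| Parent describes child | not recorded | recorded |

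Under the first reading, the form still collects the child's diagnosis (item 1), transfusion regime (item 2) and current health (item 27), but not the age or gender of the person they belong to.

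**5. What could be detected.** Respondents must be at least 18, so an age below 18 must be a child's. It can be set aside, but the parent's age is then missing. No such check exists for gender, education or occupation, or for the age of an adult child; section 4 sets no upper age for the child.

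**6. Forms concerned.** 4 centres x 30 = 120 patient/parent forms, which agrees with section 3.2. The parent share is not stated. Purely as an assumption, a share of 25% to 75% gives 0.25 x 120 = 30 to 0.75 x 120 = 90 forms with an unclear referent and no separate field for the child. If, again as an assumption, 10% to 50% of those parents described the child, 0.10 x 30 = 3 to 0.50 x 90 = 45 forms would carry the child's details. The width of these ranges shows that the documents do not determine the size.

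**The case against.** The ordinary reading of a self-completed form is that it asks about the person completing it. Annex II uses the same bare labels for age and gender, where only the respondent can be meant. Where Annex I means the child it generally says so, which suggests that Section A means the adult. The nursery option may be no more than the last step of a descending list. The investigator gives instructions, and the code on each form is repeated on the consent form, so a doubtful entry might be traced. The protocol names no comparison of children with adults.

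Much of this stands: the respondent is the likelier reading, and mixing may be uncommon. It does not remove the point. The content of the instructions is not given and none are printed in Section A. Completed forms go into a closed box, and no check at hand-in is described. The code link might show the respondent's role, but not whose details were entered. The missing age and gender of the child do not depend on anyone misreading the form.

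Three stronger readings are tempting and are not supported.

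- A reader might infer that the sample cannot be described at all. State, local government and clinic are unaffected, and diagnosis and transfusion regime have a stated referent.
- A reader might infer that a parent who enters a child's age would be judged ineligible. Nothing says that eligibility is decided from item 4, and the form is completed only after consent.
- A reader might put a figure on the bias in mean age as parent share x share entering the child's age x age gap. With a 30-year gap this runs from 0.3 x 0.1 x 30 = 0.9 to 0.7 x 0.9 x 30 = 18.9 years. All three inputs are assumed, and the result also requires that ages below 18 be averaged in unnoticed.

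**Conclusion.** The point holds in a limited form. Items 4-7 leave the referent open for parents and representatives, the nursery option does not fit the eligible respondents, and the form never asks for the child's age and gender alongside the respondent's. The consequence is possible mixing in four demographic items, only partly detectable, and the certain loss of one person's age and gender on every parent form. The needs and satisfaction items themselves are not in question. This conclusion rests on the printed form alone and assumes only that some respondents are parents or representatives, as sections 3.2 and 4 provide. How many forms would be affected cannot be derived from the documents. It is a cheap improvement worth making before the form is used, not a threat to the study as a whole.

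**What to change.** In Annex I, Section A:

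- Head items 4-7 *About you, the person completing this form*.
- Delete the nursery option from item 6. The free-text category remains for anyone it would have served.
- Add a role item: *I am: patient [ ] parent [ ] legally designated representative [ ]*.
- Add one line: *If parent or representative: child's age ___; child's gender Male [ ] Female [ ]*.

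In the report, tabulate respondent characteristics and patient characteristics separately. On patient forms the two coincide; on parent and representative forms the patient's age and gender come from the added line.

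The cost is one heading, one deleted option and two added lines before printing. A patient answers one more field, and a parent or representative answers three.

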### SECTION B

- 1. If you are a patient, what is your diagnosis? If you are a parent, what is the diagnosis of your child?**
  - A. Sickle cell disease [ ]
  - B. Sickle cell/b-thal [ ]
  - C. Sickle Beta-Plus Thalassemia [ ]
  - D. Other (please specify) \_\_\_\_\_
- 2. How is your/your child current transfusion regime?**
  - A. I am not transfused [ ]
  - B. I am regularly transfused [ ]
  - C. I am occasionally transfused [ ]
  - D. Other (please specify) \_\_\_\_\_
- 3. Where do you usually get information about Sickle Cell Disease?**
  - A. Websites
  - B. Social Networks
  - C. Scientific journals
  - D. TV
  - E. Radio
  - F. Leaflets/booklets
  - G. Doctor/nurse
  - H. Other patients
  - I. Relatives/friends
  - J. Religious leaders
  - K. Other (please specify) \_\_\_\_\_

---

**4. Please, indicate your main information source:** \_\_\_\_\_

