**21. Who pays for your treatment? (tick all that apply)**

- A. My self/my family [ ]
- B. Health insurance (private) mine [ ]
- C. Health insurance (private) my employer's [ ]
- D. State goverment provide free healthcare [ ]
- E. Other (please specify) \_\_\_\_\_

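### Annex I diagnosis item: the answer options overlap, so the counts for options A and B cannot be interpreted

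*Protocol*

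**What the plan says.** Annex I, Section B, item 1 of the Protocol asks: "If you are a patient, what is your diagnosis? If you are a parent, what is the diagnosis of your child". The printed answers are "A. Sickle cell disease", "B. Sickle cell/b-thal", "C. Sickle Beta-Plus Thalassemia" and a free-text line, "D. Other (please specify". No option is defined, and nothing says how many boxes to tick.

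For patients and parents, Section 4 sets this entry criterion on diagnosis: "Have SCD diagnosis or having a child with a SCD diagnosis". Section 5.1 states that "questionnaires will be self-completed", in private, after the investigator has explained how to fill them in. The content of that explanation is not given.

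Section 3.2 plans 30 patient/parent respondents per centre, and Section 3.3 names four centres. The Protocol describes no other source for disease type, such as genotype from the clinic record.

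**The concern.** A single-answer classification works only if exactly one option is true for each person. Here the first option restates the condition for being in the study, and the second is worded broadly enough to take in the third. Two people with the same diagnosis can truthfully give different answers, and two people with different diagnoses can truthfully give the same one.

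This is the only item on disease type. Its frequency table would mix diagnosis with the way each person read the list. The same error would pass into any breakdown by disease type of, for example, transfusion (item 2), satisfaction with treatment (item 17) or travel to other centres (item 22). An analysis plan cannot repair this afterwards, because the fault lies in what is asked.

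**Working it through.** **Inputs.** Options A to D come from Annex I, Section B, item 1. The entry criterion is in Section 4, the mode of completion in Section 5.1, and the sample size in Sections 3.2 and 3.3.

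**The plan's own figure.** 30 respondents per centre × 4 centres = 120, which agrees with the stated total.

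**Step 1: A against the entry criterion.** The Protocol uses sickle cell disease as its umbrella term throughout and nowhere narrows it to one genotype. Everyone who meets the Section 4 criterion has the disease or has a child with it. A is therefore true for 120 of 120. The form itself also treats the thalassaemia combinations as types of the disease, since it offers them to people admitted on that diagnosis.

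**Step 2: B against C.** B names sickle cell with beta-thalassaemia and does not say beta-zero or beta-plus. C names beta-plus. On the printed wording, everyone for whom C is true also fits B.

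**Step 3: true options by actual diagnosis.**

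| Actual diagnosis | Number (unknown) | Options that are true |
|---|---|---|
| Sickle cell anaemia (HbSS) | n1 | A |
| Sickle/beta-zero thalassaemia | n2 | A, B |
| Sickle/beta-plus thalassaemia | n3 | A, B, C |
| Another type | n4 | A, D |

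with n1 + n2 + n3 + n4 = 120.

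**Step 4: what truthful counts can look like.** Suppose each person ticks exactly one true option, and nobody with HbSS writes it under D.

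- A can be anything from n1 to n1 + n2 + n3 + n4 = 120.
- B can be anything from 0 to n2 + n3.
- C can be anything from 0 to n3.
- D can be anything from 0 to n4.

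A tick in A alone identifies no type. A tick in B does not separate beta-plus from other sickle/beta-thalassaemia. A tick in C or a completed D does identify the type for that person, but the totals for C and D are only lower bounds. If people tick more than one box, which the item does not forbid, the ticks can add up to more than 120.

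**Step 5: does anything else settle it?** Item 21 carries a response instruction, "Who pays for your treatment? (tick all that apply", and item 1 carries none. That might suggest that items without it are single-choice. However, item 3 (information sources) has no such instruction either, and item 4 then asks which source is the main one, so item 3 plainly expects several ticks. The absence of an instruction therefore does not establish that item 1 takes one answer. Even if it did, the choice among true options would remain open.

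**The case against.** The strongest reply is that the harm falls on an analysis nobody has planned. The study is descriptive. Its objective concerns needs and disease management in the centre, and no objective, comparison or sample size uses disease type. Transfusion and treatment satisfaction have their own items and can be reported for the whole sample whatever item 1 yields. This stands, and it limits the point to a modest one.

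A second reply is that respondents are not wholly unaided. The investigator gives instructions, and someone who sees two named thalassaemia forms may take A as the plain form and choose the most specific label that applies. That may be what the authors intended, but the Protocol does not say so, and it does not say that the instructions cover this item.

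A third reply is that a pilot is a suitable place to expose weak items. That is true, but it is no reason to print an item whose overlap can already be seen.

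A reader might infer that the sample cannot be classified by diagnosis at all, or that the share with a thalassaemia form will be understated by some stated amount. The documents support neither. Ticks in C and completed D lines still classify those respondents. The documents give no genotype distribution and no figure for how often people would choose A over a more specific option, so any percentage would only restate an assumption.

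**Conclusion.** The point holds as a minor but real defect in the instrument. A is true for all 120 planned respondents and B contains C, so the counts for A and B, and with them the distribution across the item, cannot be interpreted. The number of respondents misplaced is unknown and could be small.

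The primary objective and the sample size are unaffected. What is lost is a reliable description of the sample by disease type and any later summary on that basis. The wider survey foreseen in Section 3.2 would inherit the fault if it reused the item; the Protocol does not say whether it will.

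The conclusion rests on the printed wording and on the Protocol's use of sickle cell disease as the umbrella term. It would fall away if written instructions given with the form defined A and B as separate types.

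**What to change.** Before printing, replace the options in item 1 with mutually exclusive types and add *tick one only*. One possible list is:

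- sickle cell anaemia (HbSS)
- HbSC
- sickle/beta-thalassaemia, split into beta-zero and beta-plus only if respondents can be expected to know which they have
- other (specify)
- don't know

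The cost is one edited item. The downside is small: some *don't know* answers, and possible misreporting of subtype by lay respondents, which is why the split should be conditional. Taking the type from the clinic record through the questionnaire code would avoid self-report, but the Protocol would then have to describe that collection and the consent would have to cover it.

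If forms in the present wording have already been completed, report A as type not specified, combine B and C as sickle/beta-thalassaemia, and present that total as a lower bound.

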**5. How satisfied are you with the communication about Sickle Cell Disease and its treatment?**

- A. Very satisfied [ ]
- B. Satisfied [ ]
- C. Neither satisfied Nor dissatisfied [ ]
- D. Dissatisfied [ ]
- E. Very Dissatisfied [ ]

**6. Following your/your child Sickle Cell Disease diagnosis, who did you/your child get support from to deal with the disease?**

---

**7. How satisfied are you with the support you/your child received at the time of the diagnosis?**

- A. Very satisfied [ ]
- B. Satisfied [ ]
- C. Neither satisfied Nor dissatisfied [ ]
- D. Dissatisfied [ ]
- E. Very Dissatisfied [ ]

**8. How satisfied are you with your involvement by doctor in the decisions that affect your/your child disease?**

- A. Very satisfied [ ]
- B. Satisfied [ ]
- C. Neither satisfied Nor dissatisfied [ ]
- D. Dissatisfied [ ]
- E. Very Dissatisfied [ ]

